We used interval regressions to incorporate the theoretical bounds of the clinical outcome variables to increase the efficiency and accuracy of the imputation procedure (e.g., we restricted the imputed values of PHQ-9 to lie within the 0 to 27 intervals). We used logistic regression models to impute binary variables, and linear regression models to impute continuous variables.

For Analysis, first, we compared distributions of baseline characteristics between participants who received the PMSB intervention and participants in the usual care group, to assess the balance of the observed covariates. For each follow-up assessment, we compared the baseline covariates to detect any significant baseline differences between those who completed assessment versus those who did not.

Second, to assess the effect of the intervention, we conducted an intent-to-treat (ITT) analysis, using a multilevel, multivariate regression model to assess changes in outcome variables over time in the treatment and control groups. To account for the nature of longitudinal data, the ITT analysis was carried out by fitting multilevel mixed-effects models to allow for valid variance calculation and statistical inference. The multilevel models computed included random effects at both participant- and site-level to account for within-participant and within-site correlations, as well as robust clustered standard errors to account for within-site correlations due to participants nesting within same site. Letting  $Y_{itj}$  denote the outcome measured at time  $t$  after the baseline for participant  $i$  at site  $j$ , we estimated the following model:

$$(1) \quad Y_{itj} = \beta_{0i} + \beta_{0j} + \beta_1 Intervention_i + \beta_2 Time_t + \beta_3 Intervention_i \times Time_t + \beta_4 (Time_t - t^*) + \beta_5 Intervention_i \times (Time_t - t^*) + \beta_6 X_i + \varepsilon_{itj}$$

where the participant-specific random intercept can be written as  $(\beta_{0i} = \alpha_{00} + \omega_{0i})$  and the site-specific random intercept can be written as  $(\beta_{0j} = \gamma_{00} + \epsilon_{0j})$ . We fitted only linear models as all our outcomes were continuous.

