In the ITT analysis, individuals were assigned to the study arm to which they were randomized. Thus,  $Intervention_i$  is equal to 1 if participant  $i$  is randomized to the intervention arm and 0 otherwise.  $Time_t$  is a continuous measure of time capturing differences in months between assessment  $t$  and assessment  $t - 1$ . Because the intervention ended by the time of the 6-month assessment, we centered the time variable at 6-month follow-up in the following way:  $Time_t$  equals to -4 for 2-month follow-up, 0 for 6-month follow up, and 6 for 12-month follow-up. To model the pattern of outcome changes over time, our primary analysis employed linear spline models to divide the time axis into two segments, and within each segment consider piecewise linear trends (e.g., having a different time trend before and after the intervention ended). Specially, we denote  $t^*$  to be the month when the intervention stopped, i.e., 6 months after baseline and  $(Time_t - t^*)_+$  to be the post-intervention time trend, which equals to  $(Time_t - t^*)$  if  $Time_t > t^*$  and 0 otherwise. This choice of linear spline models allows for the ability to test whether the time trends differ before and after the intervention was finished and that treatment effect could attenuate over time once participants do not receive more intervention.

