Since the time variable is centered at 6-month follow-up, the beta coefficient on  $Intervention_i$  can be interpreted as the treatment effect on outcome levels evaluated at the end of the intervention. That is, testing for the significance of  $\beta_1$  tests the hypothesis that the treatment was more effective than enhanced usual care in improving the outcomes, as evaluated at 6 months after the baseline. The coefficient of intervention by time interaction  $\beta_3$ , tests whether the pattern of outcomes over time would be no different between treatment and enhanced usual care groups. Similarly,  $\beta_5$  tests whether changes in outcome responses over time were different between treatment and control groups after the intervention had ended. The constant term  $(\alpha_{00} + \gamma_{00})$  in equation (1) represents the level of the outcome variables in the absence of the intervention ( $Intervention_i = 0$ ) at 6-month follow-up ( $Time_t = 0$  and  $(Time_t - t^*) = 0$ ). The term  $\omega_{0i}$  denotes the participant-specific random effect,  $\epsilon_{0j}$  the site-specific random effect, and  $\varepsilon_{itj}$  denotes the

residual error term.  $X_i$  includes the baseline measure of the outcomes to control for severity of the outcome at baseline. We also estimated the effect of the intervention six months after it ended, i.e., 12-months after baseline, using the time-by-intervention interactions. Given  $Time_t = 6$  for the 12-month follow-up and  $t^* = 6$  since PMSB lasted six months, the intervention effect evaluated 12 months after baseline is given by  $\beta_1 + \beta_2 \times 6 + \beta_3 \times 6$ .

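### The printed 12-month treatment effect adds the control arm's time trend (β2) and omits the post-intervention interaction (β5), so it is not a between-arm contrast

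*Combined protocol and SAP*

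**What the plan says.** All of this is in Analytical methods, in equation (1) and the paragraphs that interpret it.

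- Equation (1) contains "\beta_1 Intervention_i + \beta_2 Time_t + \beta_3 Intervention_i \times Time_t", then a post-intervention time term with coefficient β4 and its interaction with arm, with coefficient β5.
- The arm indicator is 1 if the participant "is randomized to the intervention arm and 0 otherwise".
- Time is centred at the 6-month visit: −4 at month 2, then "0 for 6-month follow up, and 6 for 12-month follow-up".
- The spline term is zero up to the knot t*. The knot is placed at the end of the intervention so that the effect may weaken afterwards.
- The 12-month effect is said to be obtained from the interactions of time with intervention. The text then sets Time = 6 and t* = 6 and states that "the intervention effect evaluated 12 months after baseline is given by" the expression "\beta_1 + \beta_2 \times 6 + \beta_3 \times 6".
- β5 is described as a coefficient that "tests whether changes in outcome responses over time were different between treatment and control groups after the intervention had ended".

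**The concern.** A treatment effect at a given month is the intervention-arm mean minus the control-arm mean at that month. A coefficient shared by both arms cannot appear in it, yet β2 does. A coefficient that acts only in the intervention arm after month 6 must appear in it, yet β5 does not. The printed expression also conflicts with the plan's own statement that interactions are used: β2 is not an interaction, and β5 is.

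Month 12 is one of the two time points at which the plan evaluates the effect, and the one that speaks to durability. An analyst who followed the text would add any improvement in the control arm before month 6 to the treatment effect, and would extend the divergence between months 2 and 6 out to month 12 as if nothing faded. The result could be significant with no treatment effect at all.

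There is a related problem with β5. The between-arm difference in slope after month 6 is β3 + β5. β5 alone is the change in that difference at the knot.

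**Working it through.** **Inputs**, all from Analytical methods: equation (1); arm coding I = 1 or 0; centred time T = −4, 0, 6 at months 2, 6, 12; spline term s(T) equal to T minus the knot after the knot and 0 before it.

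**Contrast implied by equation (1).** The random effects and baseline covariate do not depend on arm, so

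E[Y | I=1, T] − E[Y | I=0, T] = β1 + β3·T + β5·s(T).

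β2 and β4 cancel. At month 12, T = 6 and, with the knot at month 6 (T = 0), s = 6. The effect is **β1 + 6β3 + 6β5**.

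**Can the printed expression be reproduced?** Four readings of the spline term were tried on the six arm-by-visit cells:

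| Reading | Rank (of 6) | 12-month contrast |
|---|---|---|
| Knot at T = 0, truncated at zero | 6 | β1 + 6β3 + 6β5 |
| t* = 6 taken literally on the centred scale, truncated | 4 | β1 + 6β3 |
| t* = 6, not truncated | 4 | β1 + 6β3 |
| t* = 0, not truncated | 4 | β1 + 6β3 + 6β5 |

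None gives β1 + 6β2 + 6β3, and β2 has weight zero in every row. Only the first reading lets all the coefficients be estimated. Under the second, the spline term is zero at all three visits, so β4 and β5 cannot be estimated. The plan also says that both Time and Time − t* are zero at month 6, which requires t* = 0 on the centred scale.

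**What the printed expression measures.** Write I2, I6 and C6 for the intervention means at months 2 and 6 and the control mean at month 6. In the identified model β1 = I6 − C6 and β2 + β3 = (I6 − I2)/4. Then

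β1 + 6(β2 + β3) = I6 − C6 + 1.5(I6 − I2) = **2.5·I6 − 1.5·I2 − C6**.

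No month-12 mean enters. The expression extrapolates the intervention arm's early trend and compares it with controls at month 6. Its distance from the correct contrast is 6(β2 − β5).

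**Worked examples (means and effects assumed).**

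- Both arms 10, 9, 9: the true effect is 0; printed = 22.5 − 15 − 9 = −1.5.
- Control 10, 10, 10 and intervention 9, 8, 9: the true effect is −1; printed = 20 − 13.5 − 10 = −3.5.
- Effects of 0.1, 0.4, 0.2 SD: β1 = 0.40; β3 = (0.4 − 0.1)/4 = 0.075; β5 = (0.2 − 0.4)/6 − 0.075 = −0.108. Correct = 0.40 + 0.45 − 0.65 = 0.20. Printed = 0.85 + 6β2, which is 0.85 with flat controls and 1.15 if β2 = 0.05 SD per month in the direction of benefit.

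**False-positive rate with no treatment effect.** Take unit variance, within-person correlation 0.5 (assumed) and 307/2 = 153.5 per arm. The variance of the printed contrast is (6.25 + 2.25 − 2 × 2.5 × 1.5 × 0.5 + 1)/153.5 = 5.75/153.5, so the SE is about 0.19 SD. Its bias is 6β2.

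| Control slope, months 2–6 (SD/month, assumed) | Bias (SD) | Rejection, normal approximation | Rejection, simulation (1,000 trials) | Correct contrast, simulation |
|---|---|---|---|---|
| 0.025 | 0.15 | 12% | 12.9% | 4.2% |
| 0.050 | 0.30 | 34% | 34.2% | 4.9% |
| 0.075 | 0.45 | 64% | 63.9% | 5.8% |

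For SPPB, LLFDI and WHODAS 2.0 the plan excludes 70 participants, leaving 307 − 70 = 237, or 118.5 per arm. The SE becomes √(5.75/118.5) ≈ 0.22 SD and the approximate rates fall to 10%, 28% and 53%.

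**The case against.** The printed formula itself cannot be defended. The best case on the other side concerns what follows from it.

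- **It may be only a slip in the text.** The preceding sentence says interactions were used, and β1 plus two terms multiplied by 6 is the shape of the correct contrast. The code may have been right. This stands: the documents do not show which contrast was run, so the error is in the written rule, and a wrong reported result is possible but not shown.
- **Other analyses are free of it.** The 6-month effect (β1), the joint global test of the 6-month effects, and sensitivity model (3), which takes the 12-month effect from a single interaction coefficient, do not use this formula. This also stands. A large distortion should show up against model (3), but a sensitivity analysis does not correct the primary one.
- **β5 alone is a legitimate test.** It does test whether the between-arm slope difference changes at the knot, which fits the stated purpose of comparing trends before and after the intervention. But the sentence describing β5 speaks of differences between arms in change after the intervention ended, and that quantity is β3 + β5. This is the lesser part of the point.
- **The sizes are illustrative.** The slopes, effects and correlation are assumed, and the rates for 307 participants overstate the problem for the three physical outcomes. The direction of the problem does not depend on these choices.

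**Conclusion.** The concern holds. As written, the 12-month rule is wrong: β2 does not belong in it under any reading of t*, and β5 is missing under the only reading in which the spline model can be estimated. The error is 6(β2 − β5), which vanishes only if β2 happens to equal β5. Under the stated assumptions it turns a true 0.20 SD into 0.85 SD or more, and raises a nominal 5% error rate to between about 12% and 64% with 307 participants, or about 10% to 53% with 237. Those figures depend on the assumed control slopes and correlation; the algebra does not. Because the rule governs a main reported time point and misleads if followed, it must be corrected. The 6-month result is not affected.

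**What to change.** 1. Replace the 12-month expression with β1 + 6β3 + 6β5, with its standard error from the full covariance matrix of the coefficients (in Stata, a lincom statement).
2. Define t* = 0 on the centred time scale, remove the statement that t* = 6 beside centred Time = 6, and show the truncation at zero in the spline terms of equations (1) and (2).
3. Test the between-arm difference in post-intervention change as β3 + β5 = 0, and describe β5 as the change in the between-arm slope difference at month 6.
4. Check the analysis code first. Re-run every 12-month result that used the printed formula; if the code already used the correct contrast, only the text changes.

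The cost is a few lines of text, one changed linear-combination statement and a code check. No new data are needed.

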Although missing a follow-up assessment did not seem to be related to participants’ demographic characteristics, to account for missing data we used multiple imputation methods in Stata version 15.1 via the *mi impute chained* command (5). Multiple imputation was carried out in three steps. First, we imputed the missing data for all the variables considered, creating 20 imputed datasets each one consisting of 307 participants with three follow-up assessments per participant. In the second step we ran analysis on each individually imputed data set. Finally, we aggregated the individual estimates to obtain final estimates and adjusted standard errors for the uncertainty due to imputation (6).

Each imputation was carried out using the chained equations method (7). In what follows, we refer to variables with missing data as incomplete variables and those with non-missing data as complete variables. Each incomplete variable  $x_j$  was specified as a conditional function ( $g_j$ ) given the set of all other variables used in the imputation, comprising both incomplete ( $x_1, \dots, x_m$ ) and complete variables ( $Z$ ). We fitted the conditional model  $g_j$  to generate the predicted values of  $x_j$  using an iterative method. Specifically, each incomplete variable  $x_j$  was iteratively estimated and in each iteration the variable  $x_j^t$  was then updated to  $x_j^{t+1}$  based on the conditional model. This updated variable was then used in the estimations of the other variables, following the conditional model specification

$$x_j^{t+1} \sim g_j(x_j \mid x_1^{t+1}, \dots, x_{j-1}^{t+1}, x_{j+1}^t, \dots, Z, \phi_j),$$

for  $j \in \{1 \dots m\}$ , where  $\phi_j$  were parameters of the conditional model  $g_j$ . These steps were repeated for all variables  $x_1, \dots, x_m$  and, after an initial burn-in phase, the procedure was stopped once convergence was reached.

The variables used for imputation included main outcome variables and their baseline measures, participant socio-demographics, clinical characteristics, and study design variables, such as site and intervention indicators, as well as dummy indicators for each follow-up assessment.

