In assessing the effectiveness of PMSB on physical function outcomes (SPPB (8), LLFDI and WHODAS 2.0 (9)), 35 participants in the intervention condition were excluded from the analysis because they could not receive the Strong Bodies treatment due to lack of medical clearance (9 participants), death (2 participants), medical condition (e.g., surgery, knee replacement; 5 participants), lack of access to facilities following the hurricanes in Florida and Puerto Rico (18 participants), or they had to be referred to treatment due to active suicidality (1 participant). Their control counterparts, according to the 2-person block randomization, were also excluded to rebalance the sample. We applied this exclusion because the lack of sessions in Strong Bodies was not related to the intervention but to these other external factors. In total, 70 participants were excluded in all analyses where the outcomes were physical function measures. We confirmed that baseline characteristics between control and intervention participants remained balanced after this exclusion.

We conducted four sets of sensitivity analyses. First, to account for multiple outcome assessment, we estimated a multivariate multilevel regression (10) to test treatment effects obtained from a joint model instead of modeling the outcomes separately. This strategy accounts for the correlation among outcomes and provides more powerful tests of treatment effects compared to more traditional approaches (e.g., Bonferroni adjustments or combining the outcomes into a composite measure)(11). To estimate this multivariate model, we created a long data set where each outcome (SPPB, LLFDI, WHODAS 2.0, HSCL-25 and GAD-7) at each follow-up assessment (2-, 6-, and 12-months) was stacked for each individual, meaning a data set where each participant had 15-observations (five outcomes times three follow-up assessments). The values for each outcome were combined into a single outcome variable  $Y_{hitj}$ , where  $h$  indexes the outcome measure. Instead of estimating equation (1) separately for each outcome, we produced a single equation

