$$(2) \quad Y_{hitj} = \beta_{0hi}Outcome_h + \beta_{0hj}Outcome_h + \beta_{1h}Intervention_i \times Outcome_h \\ + \beta_{2h}Time_t \times Outcome_h + \beta_{3h}Intervention_i \times Time_t \times Outcome_h \\ + \beta_{4h}(Time_t - t^*) \times Outcome_h + \beta_{5h}Intervention_i \times (Time_t - t^*) \times Outcome_h \\ + \beta_{6h}X_i \times Outcome_h + \varepsilon_{hitj}Outcome_h$$

where  $h = 1$  for SPPB,  $h = 2$  for LLFDI,  $h = 3$  for WHODAS 2.0,  $h = 4$  for HSCL-25, and  $h = 5$  for GAD-7. Since the time variable is centered at 6-month follow-up, the beta coefficients on  $Intervention_i \times Outcome_h$ ,  $\beta_{1h}$ , can be interpreted as the treatment effect on outcome  $h$  evaluated at the end of the intervention. After modeling the outcomes jointly, we conducted a joint global test to evaluate the null hypothesis that all treatment effects were zero, i.e.,  $\beta_{11} = \beta_{12} = \beta_{13} = \beta_{14} = \beta_{15} = 0$ . This joint test considers the correlation among measures, which is likely to be different from zero in our context, e.g., participants with low SPPB scores are likely to also self-report lower LLFDI scores.

Second, we examined whether our intent-to-treat results were robust to more traditional models that included only an indicator for intervention, three indicators of time (2-, 6- and 12-months) and their two-way interactions using the following model:

$$(3) \quad Y_{itj} = \beta_{0i} + \beta_{0j} + \beta_1Intervention_i + \beta_{21}Time_1 + \beta_{22}Time_2 + \beta_{23}Time_3 \\ + \beta_{31}Intervention_i \times Time_1 + \beta_{32}Intervention_i \times Time_2 \\ + \beta_{33}Intervention_i \times Time_3 + \varepsilon_{itj}$$

where  $Y_{itj}$  denotes the outcome measured at baseline, 2-, 6- and 12-months ( $t = 0, 1, 2,$  and  $3,$  respectively) for participant  $i$  at site  $j$ ,  $Time_1, Time_2, Time_3$  are indicator variables for the 2-, 6- and 12-month follow-ups, respectively (baseline is the reference period), and  $Intervention_i \times Time_1, Intervention_i \times Time_2, Intervention_i \times Time_3$  are the two-way interactions between the intervention indicator and the time indicators. The coefficient  $\beta_{32}$  represents the effect of PMSB at the end of the intervention (6-months), while  $\beta_{33}$  represents the effect of PMSB six-months post-intervention (12-months).

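### The SPPB, LLFDI and WHODAS 2.0 analyses carry the intent-to-treat label but drop 70 of 307 participants on a criterion that only the intervention arm can trigger

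*Combined protocol and SAP*

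**What the plan says.** All of the relevant text is in the Analytical methods section of the combined protocol and SAP.

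- **Label.** The plan states that "to assess the effect of the intervention, we conducted an intent-to-treat (ITT) analysis". It defines this by randomised arm, "In the ITT analysis, individuals were assigned to the study arm to which they were randomized", and exempts no outcome.
- **Exclusion.** For SPPB, LLFDI and WHODAS 2.0, "35 participants in the intervention condition were excluded from the analysis because they could not receive the Strong Bodies treatment". The reasons given are hurricane access (18), no medical clearance (9), a medical condition (5), death (2) and active suicidality (1). Then: "Their control counterparts, according to the 2-person block randomization, were also excluded to rebalance the sample".
- **Scope.** "70 participants were excluded in all analyses where the outcomes were physical function measures".
- **Justification.** The plan argues that the reasons were external to the intervention and that baseline characteristics stayed balanced.
- **Label used again.** After describing the exclusion, the plan says "we examined whether our intent-to-treat results were robust to more traditional models".

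None of the four sets of sensitivity analyses is stated to bring the 70 back for a physical-function outcome. The compliance analyses leave out the same 70.

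**The concern.** Whether Strong Bodies could be received is known only after assignment and only in the intervention arm. A control who died, had surgery or would have been refused clearance stays in the analysis unless the other member of the block happened to be excluded. The control partner leaves because of someone else's status, so pairwise removal equalises the counts and does nothing for prognosis. A baseline balance check cannot detect selection on events that come later.

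Three of the five modelled outcomes are affected. A reader told that they are intent-to-treat will take them as the effect of being assigned to the programme. They instead describe a subset from which intervention participants with certain health problems have been removed, along with others who could not be treated.

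**Working it through.** **Counts.** 18 + 9 + 5 + 2 + 1 = 35 and 2 × 35 = 70, which reproduces the plan's figures. 70/307 = 22.8%, and 307 − 70 = 237 remain. Health-related reasons: 9 + 5 + 2 + 1 = 17 (49% of 35). Hurricane access: 18 (51%).

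**Inputs not in the plan.**
- 307 is given as the size of each imputed data set and is not expressly called the number randomised. It is the only full-sample figure, so I use it.
- Arm sizes are not given. Two-person blocks imply 1:1, so I assume 307/2 = 153.5 per arm, with 153.5 − 35 = 118.5 retained.
- δ is how much worse, in SD after baseline adjustment, the health-excluded would score than the rest of their arm. No outcomes are reported for them, so δ is assumed: 0, 0.3, 0.5 and 1.0.

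**Does removing partners restore comparability?** Randomisation would put about 17 controls with comparable health problems in the other arm. Removing 35 controls without regard to their own health takes out 17 × 35/153.5 = 3.9 of them and leaves about 13.1. All 17 such intervention participants leave.

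**Bias under no true effect.** The retained intervention arm has none of this group. The retained control arm keeps a share of 13.1/118.5 = 17/153.5 = 0.111. The difference in favour of the intervention is therefore 0.111δ. Two narrower counts are worth showing:
- 14 cases, leaving out the deaths and the suicidality case: 14/153.5 = 0.091δ.
- 5 cases, further assuming that baseline adjustment removes the whole difference for the 9 without clearance: 5/153.5 = 0.033δ.

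**Chance of a false significant benefit.** With a simple SE of sqrt(4/237) = 0.130 SD, this is 1 − Φ(1.96 − bias/0.130), against a nominal 2.5%.

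| Cases counted | δ = 0 | δ = 0.3 | δ = 0.5 | δ = 1.0 |
|---|---|---|---|---|
| 17: bias (SD) | 0 | 0.03 | 0.06 | 0.11 |
| 17: false benefit | 2.5% | 4.4% | 6.3% | 13.4% |
| 14: bias (SD) | 0 | 0.03 | 0.05 | 0.09 |
| 14: false benefit | 2.5% | 4.0% | 5.4% | 10.4% |
| 5: bias (SD) | 0 | 0.01 | 0.02 | 0.03 |
| 5: false benefit | 2.5% | 3.0% | 3.3% | 4.4% |

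A simulation supports the bias formula. It used 8,000 trials per scenario, 153 pairs, health events equally likely in both arms, random hurricane exclusions, partners dropped, and adjustment for baseline. Mean bias was about 0.00 SD at δ = 0, 0.055 to 0.056 at δ = 0.5 and 0.110 to 0.111 at δ = 1.0.

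**Change of estimand, a separate matter from bias.** If the 35 would gain nothing in function, the as-randomised effect is 118.5/153.5 = 0.772 of the effect in those retained, and 1/0.772 = 1.295. If they would gain half, it is 0.772 + 0.5 × 0.228 = 0.886.

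**Precision.** The exclusion raises the SE by up to sqrt(307/237) = 1.138, about 14%.

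**The case against.** The strongest defence has four parts.

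1. *The rule is disclosed.* Every reason has a count, a rationale is given, and the paragraph on the exclusion does not itself use the ITT label. This stands as to openness. The general label still exempts no outcome, is used again afterwards, and comes with no stated full-sample result.
2. *Most exclusions are external.* The 18 hurricane cases are just over half. If block partners shared site and calendar period, which the plan does not say, dropping whole pairs for an outside shock leaves the comparison in the other pairs intact. This largely stands as to bias under the null. It does not make the analysis ITT. The Descriptive methods section also provides a home video for people unable to attend in person, so loss of facilities is partly a matter of how the programme was delivered.
3. *The bias is small and assumed.* Direction is inferred, and some conditions, such as a knee replacement, could improve later function. The timing of clearance is not stated; if it reflected pre-existing conditions, adjustment for the baseline outcome would remove part of that difference. The 5-case row shows how little may remain. This stands as to size.
4. *The SE is not the model's.* The simple formula ignores baseline adjustment, repeated measures and site clustering. This also stands: the false-benefit rates are illustrative.

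None of this supplies an analysis of everyone as randomised.

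**Conclusion.** The concern holds. The three physical-function analyses are not intent-to-treat, and that conclusion rests on the text alone. The direction of bias from the 17 health-related exclusions is likely, though not certain, to favour the intervention. Its size depends on an assumed δ: 0.03 to 0.11 SD on 17 cases, 0.03 to 0.09 SD on 14, and 0.01 to 0.03 SD on 5, for δ from 0.3 to 1.0. The estimate in those retained exceeds the as-randomised effect by up to about 30%. That is a ceiling, because it needs all 35 to gain nothing although Positive Minds may still have helped them.

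The case for changing the plan rests on the conflict with the label and the missing full-sample result, more than on any one figure for bias. The main HSCL-25 and GAD-7 analyses are not affected.

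**What to change.** - Make the primary analysis of SPPB, LLFDI and WHODAS 2.0 the one that includes all 307 as randomised.
- State a strategy for deaths that applies to both arms, and do not treat imputed function after death as observed. One option is to analyse function measured while alive and report deaths by arm.
- Keep the 237-participant analysis as a supplementary analysis, labelled non-ITT.
- Fit joint model (2) on the full randomised set and say so. The plan describes "a data set where each participant had 15-observations" but does not say whether the 70 leave that model entirely or keep some rows.
- Optional: a worst-score sensitivity analysis for deaths, and one that excludes hurricane-affected sites and calendar periods in both arms.

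The cost is a re-run of three outcomes and model (2). The data are already prepared, since the plan describes "creating 20 imputed datasets each one consisting of 307 participants with three follow-up assessments per participant". The extra work is to identify follow-ups that fall after a death, because the definition of complete missing data covers only withdrawal and loss to follow-up. The physical-function effect will probably come out somewhat smaller.

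### The global test offered as the account for five outcomes supports only an overall 6-month conclusion; it does not protect claims about single outcomes or cover the 12-month effects

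*Combined protocol and SAP*

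**What the plan says.** All references are to the Analytical methods section of the combined protocol and SAP.

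- **Main analysis.** Equation (1) is fitted to each outcome on its own. Testing the intervention coefficient (beta_1) is described as the test of whether treatment beats enhanced usual care at 6 months. On the later time point the text adds: "We also estimated the effect of the intervention six months after it ended".
- **Multiplicity.** The subject appears once, after the sentence "We conducted four sets of sensitivity analyses". The first of these is introduced as follows: "First, to account for multiple outcome assessment, we estimated a multivariate multilevel regression (10) to test treatment effects obtained from a joint model". The plan says this gives more powerful tests of treatment effects "compared to more traditional approaches (e.g., Bonferroni adjustments or combining the outcomes into a composite measure".
- **Joint model.** The data set is one "where each outcome (SPPB, LLFDI, WHODAS 2.0, HSCL-25 and GAD-7) at each follow-up assessment (2-, 6-, and 12-months) was stacked for each individual", which gives 5 × 3 = 15 rows per participant. The plan continues: "Instead of estimating equation (1) separately for each outcome, we produced a single equation" (equation 2).
- **Test.** From that fit, "we conducted a joint global test to evaluate the null hypothesis that all treatment effects were zero", written out as beta_11 = beta_12 = beta_13 = beta_14 = beta_15 = 0. The text defines each beta_1h as the effect on outcome h at the end of the intervention, that is, at 6 months.

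The section names no single primary outcome, testing order, alpha level, adjusted p-value or closed procedure. It gives no joint test at 12 months.

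**The concern.** The plan accepts that five outcomes call for some account of multiplicity, and it sets its method against Bonferroni on power. The two answer different questions. Bonferroni licenses a statement about each outcome it rejects. A 5-degree-of-freedom global test licenses one statement, that the five effects are not all zero. This is weak control: error is held only when every null is true. Once one outcome responds, the global test tends to reject, and it then says nothing about the other four. Modelling the correlation between outcomes does not adjust the individual beta_1h p-values either.

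At stake is how results for SPPB, LLFDI, WHODAS 2.0, HSCL-25 and GAD-7 are read one by one. A reader told that multiple outcomes were accounted for may take each significant coefficient as protected. At 12 months the gap is wider, because none of the interaction terms that carry the 12-month effect enters the global null.

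**Working it through.** **Inputs from the documents.** Five outcomes; effects of interest at 6 and 12 months; a global null of five 6-month coefficients. The plan states no error rate, so there is no figure of its own to reproduce.

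**Assumptions.** Two-sided 5% per outcome. The five z-statistics are multivariate normal with one common correlation ρ of 0, 0.3, 0.5 or 0.7; the plan says only that the correlation is likely to differ from zero. Real effects have mean z of 4 or 5. Each simulation uses 400,000 draws.

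**Step 1: five unadjusted tests, all nulls true, no gate.** With independence, 1 − 0.95^5 = 22.6%. With correlation, see the table.

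**Step 2: the global test as a gate.** The gate opens if z′R⁻¹z exceeds the 95th percentile of chi-square on 5 df, where R is the correlation matrix. Outcomes are then read at 5% each. The plan does not state this rule; it is the reading most favourable to the plan.

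**Step 3: Holm for comparison.** Ordered p-values are compared with 0.05/5, 0.05/4, 0.05/3, 0.05/2 and 0.05.

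Chance of at least one false outcome claim:

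| Scenario at 6 months | ρ = 0 | 0.3 | 0.5 | 0.7 |
|---|---|---|---|---|
| All five null, no gate | 22.6% | 21% | 18% | 15% |
| All five null, gated | 4.9% | 4.5% | 3.9% | 3.3% |
| One real effect (z = 5), gated | 18.5% | 17% | 16% | 13% |
| One real effect (z = 5), Holm | 4.9% | 4.6% | 4.3% | 3.6% |
| Two real effects (z = 4), gated | 14.3% | 14% | 13% | 11% |
| Two real effects (z = 4), Holm | 4.8% | 4.5% | 4.1% | 3.5% |

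The gate opens in 98.5–100% of trials with one real effect and in at least 99.7% with two. At ρ = 0 the gated figures match the closed forms for the remaining nulls: 1 − 0.95^4 = 18.5% and 1 − 0.95^3 = 14.3%. A single weaker effect (z = 3) still gives about 13–16% gated, so the result does not depend on a large effect.

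**Step 4: 12 months.** If 6-month effects exist, the 6-month test opens and does not limit error at 12 months. Five true 12-month nulls, each tested at 5%, then give about 15–23% over the same range of ρ.

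**Step 5: the printed 12-month contrast.** In equation (1) the difference between arms at a given time is beta_1 + beta_3 × Time + beta_5 × (Time − t*)₊. The common slope beta_2 is the same in both arms and cancels. The text prints beta_1 + beta_2 × 6 + beta_3 × 6, which includes beta_2 and omits beta_5. The coding of the knot also matters. With Time = 6 and t* = 6 as printed, the spline term is zero at 12 months. With the knot at the 6-month visit on the centred scale (Time = 0), it equals 6. No 12-month test can be specified until this is settled.

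**The case against.** The strongest defence is that the plan never promises family-wise control for each outcome. It lists the joint model among its sensitivity analyses and writes out the exact null, and the test delivers what that null says. This stands. A reader might infer that the plan claims outcome-level control and fails to deliver it, but the documents do not go that far. What they do is give the joint model the purpose stated in "First, to account for multiple outcome assessment, we estimated a multivariate multilevel regression" and prefer it to Bonferroni, with nothing else in the section doing that job.

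Second, a reader might quote 22.6% for five tests, or 40.1% for ten independent tests (1 − 0.95^10), as the error of the plan's procedure. Those figures ignore the global test and assume that every null is true. If it is used as a gate and all five 6-month nulls are true, the 6-month error is at most 5%. Full independence is also implausible when the same outcomes are measured twice: with an assumed correlation of 0.6 between time points, ten tests give about 25–37%. The gated figures are the fair ones to lead with at 6 months.

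Third, unadjusted testing is inferred from silence. No alpha or decision rule is printed, and the 12-month effects are said to be estimated. So the point is that no protection is described, not that particular false claims were made.

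Fourth, some statisticians would not adjust across five distinct, separately reported outcomes. That position is arguable, but this plan does not take it: it sets out to account for multiple outcomes.

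**Conclusion.** The concern holds in this form. The global test supports the statement that at least one 6-month effect is non-zero. It does not support claims about individual outcomes, is not stated to gate them, and does not reach 12 months. Even when it is credited as a gate, false outcome claims occur in about 11–14% of trials with two real effects and 13–19% with one, against about 3–5% with Holm. Without the gate, five null tests give about 15–23%.

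These sizes rest on an assumed two-sided 5%, correlations of 0 to 0.7 and mean z of 4 or 5. The direction follows from the form of the null and does not depend on those values. This is a worthwhile and inexpensive improvement. It does not show that any reported result is wrong.

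**What to change.** 1. State that the global test from equation (2) supports an overall 6-month conclusion only.
2. Report Holm-adjusted p-values for the five 6-month effects beside the unadjusted ones, and base outcome-level claims on the adjusted values. The smallest p-value is then compared with 0.05/5 = 0.01.
3. A closed Wald procedure built on equation (2) is an alternative with strong control. It is not equivalent to Holm and may reject different outcomes. It involves 2^5 − 1 = 31 intersection hypotheses, each pooled over the 20 imputed data sets.
4. For 12 months, first reconcile the printed contrast and the knot coding with equation (1). Then either apply Holm across all ten tests (first step 0.05/10 = 0.005), or use a separate 12-month Holm family and state that error is controlled per time point only. Two families at 5% each allow up to 10% across both.

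**Cost.** Steps 1 and 2 need a few sentences and p-values the analysis already yields. Some p-values become less favourable. Because the document describes the analyses as completed, the adjustment should be labelled as added afterwards. Which participants enter the physical-function analyses is a separate issue, and this change does not depend on it.
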